6.2. General Methodology

6.2.1. Overview

This study follows patients with drug refractory symptomatic persistent AF who treated by cryoballoon ablation of the pulmonary veins for 12 months. The two co-primary endpoints of the study focus on the safety of the procedure and efficacy of the procedure in treating AF. The efficacy endpoint is subject to a three-month blanking period in accordance with the current FDA guidance¹.

1

<https://www.fda.gov/medicaldevices/deviceregulationandguidance/guidancedocuments/ucm182016.htm#s6>

The analysis described in this SAP will be conducted by Medtronic statisticians. Efficacy endpoints will be adjudicated by a core lab. Safety endpoints will be adjudicated by the Clinical Event Committee (CEC). Determination of events and event onset dates used in the PMA supplement, PMDA submission, and any resulting publications will be based on the core lab and CEC adjudications. CEC determinations will also be used to determine AE severity and procedure or device-relatedness. Prior to evaluation of the study's primary objectives, a descriptive analysis will be performed. Demographic and other key baseline characteristics will be summarized for the mITT dataset.

6.2.2. Primary Efficacy Objective

Demonstrate an acceptable efficacy success rate at 12 months after the pulmonary vein isolation (PVI) ablation procedure.

6.2.2.1. Hypothesis

The following hypothesis will be tested in a one-sided test at the 0.025 significance level:

Ho: $ns \leq 40\%$

Ha: $ns > 40\%$

where ns is the probability of treatment success at 12 months.

6.2.2.2. Endpoint Definition

Treatment success is defined as freedom from treatment failure. Treatment failure is defined as any of the following components:

- Acute procedural failure
- Documented AF/AT/ AFL on Holter/TTM/12-lead ECG after the 90 day blanking period
 - Minimum of 30 seconds on Holter/TTM and 10 seconds on 12-lead ECG
- A reablation for the treatment of recurrent AF/AT/AFL after the 90 day blanking period
- Class I or III antiarrhythmic drug (AAD) dose increase from the historic maximum ineffective dose (prior to the ablation procedure) or initiation of a new Class I or III AAD after the 90 day blanking period. Note: remaining on the same pre-ablation dose or decreased dose, or re-initiation of a previously failed or not tolerated Class I or III AAD after the 90 day blanking is not considered a failure. Subjects are allowed to remain on Class I or III antiarrhythmic medications at the historic maximum ineffective dose (on prior to the ablation procedure) after the 90 day post-procedure blanking period.
- Ablation using RF in the left atrium

Blanking period is defined as the first 90 days after the index ablation procedure. Recurrences of atrial arrhythmias during the blanking period will not be counted in the determination of the first clinical failure for the primary endpoint. Within the blanking period, recurrent arrhythmias can be managed with antiarrhythmic drugs, cardioversion or one cryo re-ablation procedure of the pulmonary veins. Titration of Class I and III antiarrhythmic medications are allowed during the blanking period.

Acute procedural failure is defined as:

- Inability to isolate all accessible targeted pulmonary veins (minimally assessed for entrance block and, where assessable, exit block) during the index procedure
- Left atrial non-PVI ablations including but not limited to, ablation of linear lesions, complex fractionated electrograms or non-PV triggers

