6.2. Endpoints

6.2.1. Primary Endpoints

1. Primary Efficacy: Demonstrate an acceptable efficacy success rate at 12 months after the pulmonary vein isolation (PVI) ablation procedure.

Treatment success is defined as freedom from treatment failure. Treatment failure is defined as any of the following components:

- Acute procedural failure
- Documented AF/AT/AFL on Holter/TTM/12-lead ECG after the 90 day blanking period
 - Minimum of 30 seconds on Holter/TTM and 10 seconds on 12-lead ECG
- A reablation for the treatment of recurrent AF/AT/AFL after the 90 day blanking period

- Class I or III antiarrhythmic drug (AAD) dose increase from the historic maximum ineffective dose (prior to the ablation procedure) or initiation of a new Class I or III AAD after the 90 day blanking period. Note: remaining on the same pre-ablation dose or decreased dose, or re-initiation of a previously failed or not tolerated Class I or III AAD after the 90 day blanking is not considered a failure.
- Ablation using RF in the left atrium

Blanking period is defined as the first 90 days after the index ablation procedure. Recurrences of atrial arrhythmias during the blanking period will not be counted in the determination of the first clinical failure for the primary endpoint. Within the blanking period, recurrent arrhythmias can be managed with antiarrhythmic drugs, cardioversion or one cryo re-ablation procedure of the pulmonary veins. Titration of Class I and III antiarrhythmic medications are allowed during the blanking period. Subjects are allowed to remain on Class I or III antiarrhythmic medications at the historic maximum ineffective dose (on prior to the ablation procedure) after the 90 day post-procedure blanking period.

Acute procedural failure is defined as:

- Inability to isolate all accessible targeted pulmonary veins (minimally assessed for entrance block and, where assessable, exit block) during the index procedure
- Left atrial non-PVI ablations including but not limited to, ablation of linear lesions complex fractionated electrograms or non-PV triggers

2. Primary Safety: Demonstrate an acceptable safety profile of the pulmonary vein isolation (PVI) ablation procedure.

A primary safety event is defined as a serious procedure-related or serious system-related adverse event including the following:

- Transient ischemic attack (within 7 days of ablation procedure)
- Cerebrovascular accident (within 7 days of ablation procedure)

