13.7. Medications

It is recommended to discontinue the use of Class I and III antiarrhythmic medication by the end of the 90 day post-procedure blanking period. Up-titration of the dose is allowed only in the 90 day post-procedure blanking period.

Information regarding medications prescribed for anticoagulation or to treat atrial arrhythmias, including the medication name, purpose for use, start and stop dates, and route of administration, will be collected from subject enrollment through study exit.

13.7.1. Class I and III antiarrhythmic medication use after the 90 day post-procedure blanking period

- Subjects are allowed to remain on Class I or III antiarrhythmic medications at the historic maximum ineffective dose (on prior to the ablation procedure) after the 90 day post-procedure blanking period.
- Subjects may re-initiate, at any point during follow-up, a Class I or III antiarrhythmic medication that failed or was not tolerated prior to the ablation procedure at the same or lower dose.
- Initiation of a new Class I or III antiarrhythmic medication after the 90 day post-procedure blanking period will be treated as a primary endpoint failure.
- Remaining on a dose higher than the historic maximum ineffective dose (on prior to the ablation procedure) after the 90 day post-procedure blanking period will be treated as a primary endpoint failure.

All medications are permitted in the study with the exception of investigational drugs that may confound the study results.

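### A never-used Class I/III drug started in blanking and continued past day 90 escapes the SAP's failure list but may fail under Protocol 13.7.1, and no text says which applies

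*SAP*

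**What the plan says.** The primary efficacy definition appears in SAP 6.2.2.2, Protocol 6.2.1 and Protocol 17.3.1. In each, the drug component has two limbs. One is a dose increase over the highest dose that was ineffective before ablation. The other is "initiation of a new Class I or III AAD after the 90 day blanking period".

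On timing, "Blanking period is defined as the first 90 days after the index ablation procedure". On treatment in that window: "Within the blanking period, recurrent arrhythmias can be managed with antiarrhythmic drugs, cardioversion or one cryo re-ablation procedure of the pulmonary veins". Nothing restricts these drugs to ones the subject had already taken. Eligibility requires failure or intolerance of only one Class I or III drug, so untried agents may remain.

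Protocol 13.7.1 covers use after blanking. Its third bullet repeats the start-date test: "Initiation of a new Class I or III antiarrhythmic medication after the 90 day post-procedure blanking period will be treated as a primary endpoint failure". Its fourth bullet adds a second failure: "Remaining on a dose higher than the historic maximum ineffective dose (on prior to the ablation procedure) after the 90 day post-procedure blanking period". That carry-over rule is in none of the three endpoint lists.

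The only uses after blanking that are expressly exempt are staying at or below the pre-ablation dose and restarting a drug that had failed or was not tolerated. On stopping, Protocol 13.7 gives advice only: "It is recommended to discontinue the use of Class I and III antiarrhythmic medication by the end of the 90 day post-procedure blanking period".

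**The concern.** The new-drug limb asks when the drug began, not whether it is in use while the endpoint is being assessed. The same new drug is a failure if begun on day 91 and is not listed as one if begun on day 50 and taken to month 12. In the second case the drug may have been given because the arrhythmia had recurred, and it may be what keeps later monitoring clean.

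This is the primary endpoint of a single-arm, unblinded study tested against a fixed 40% goal, and the investigator decides when a drug starts. Counting these subjects as successes can only raise the success rate. The sponsor's own statisticians run the analysis, so a rule left open could be settled with outcomes visible.

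**Working it through.** **The plan's own figure.** SAP 7.1 uses an exact binomial test of 40% against 54%, one-sided 0.025, with 150 × (1 − 0.10) = 135 analysed. The smallest r with P(X ≥ r | 135, 0.40) ≤ 0.025 is 66. Alpha is 0.0224 and power is P(X ≥ 66 | 135, 0.54) = 0.899, as printed. For the PMDA cohort (n = 148, r = 72) alpha is 0.0202 and power 0.917, also as printed. No printed figure is in dispute.

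**The rules side by side.**

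| Subject | Three endpoint lists | Protocol 13.7.1 |
|---|---|---|
| New drug started day 91 | Failure (new-drug limb) | Failure (third bullet) |
| Pre-ablation drug kept at or below its historic maximum | Not a failure | Not a failure |
| New drug started day 50, continued to month 12 | New-drug limb not met; dose limb has no historic dose to compare with; so not a listed failure | Third bullet not met; fourth bullet met if the historic maximum is zero, not evaluable if it is undefined |

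Only the last row is unsettled. No passage defines the historic maximum for a drug never taken.

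**Pass mark under the planned test.** SAP 6.2.2.3 uses Kaplan-Meier with Greenwood's formula and a log-log interval. With n = 150 and no censoring, S = x/150, SE = √(S(1 − S)/150), θ = SE/(S·|ln S|), and the lower bound is S^exp(1.96θ).

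- x = 73: S = 0.4867, SE = 0.0408, θ = 0.1164, lower bound 40.46%. Passes.
- x = 72: S = 0.4800, SE = 0.0408, θ = 0.1158, lower bound 39.81%. Does not pass.

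**Effect of counting the subjects as successes.** Each one moves the estimate by 1/150 = 0.67 points. Let q be the share of treated subjects who would be failure-free but for a new drug started in blanking and continued. The documents give no value, so q is assumed. If the true rate without them is 40%, the chance of passing is P(X ≥ 73 | 150, 0.40 + q). The last column repeats this with the plan's n = 135 and r = 66.

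| q | Subjects of 150 | n = 150, no censoring | n = 135 (plan's approximation) |
|---|---|---|---|
| 0 | 0 | 1.9% | 2.2% |
| 2% | 3 | 5.9% | 6.3% |
| 4% | 6 | 14.3% | 14.5% |
| 6% | 9 | 28.3% | 27.8% |

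**Effect of counting them as failures.** If the planning value of 54% had included a 2% share of such subjects as successes, the rate becomes 52% and power at n = 135 falls from 89.9% to 79.1%.

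**The case against.** The strongest reply is that Protocol 13.7.1 already deals with the case. A drug never taken has no pre-ablation dose. If that is read as zero, any dose exceeds it and the fourth bullet makes the subject a failure. The exemptions point the same way, since a newly started drug fits neither of them. This stands as a possible reading. It does not settle the matter, because the fourth bullet refers to an ineffective dose that the subject was on before ablation, no passage equates its absence with zero, and the SAP list that will be programmed omits the rule.

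A second reply is that the drug component is a design choice. The version history records that the post-blanking dose rule was changed on FDA feedback. The documents also do not say that the endpoint must exclude all drug help beyond what had already failed. Restarting a drug that was merely not tolerated is exempt, and such a drug need not have been ineffective. This too stands, so the point should not rest on an inferred intent. It rests on the difference between the lists and 13.7.1, and on the missing definition.

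Third, the size is hypothetical. The advice to stop by day 90 should make the pattern less common, and each subject matters only if otherwise failure-free under weekly transmissions, two Holters and ECGs. That is correct. But the advice is not binding and does not classify anyone who continues.

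**Conclusion.** The gap is real, and the classification is ambiguous rather than settled. Under the SAP list as written, a never-used drug started in blanking and continued to month 12 is not a failure. Under Protocol 13.7.1 it is one if the historic maximum is taken as zero. The documents do not choose.

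A reader might infer that this subject meets no failure rule anywhere and is certain to be counted as an ablation success. The documents do not support that, because the fourth bullet of 13.7.1 is a failure rule that can reach the case. Nor do they support reading 5.9% to 28.3% as the trial's actual false-positive rate. Those figures assume a 2% to 6% frequency, a true rate of exactly 40% without these subjects, and no censoring.

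What is established is the direction, which favours the device, and that a handful of subjects could matter near the pass mark. This should be fixed before analysis. With the frequency unknown and one possible failure rule already in the Protocol, it does not rank as a must-fix.

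**What to change.** For endpoint counting only, reconcile SAP 6.2.2.2 with Protocol 6.2.1, 13.7.1 and 17.3.1 before analysis:

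- Carry the 13.7.1 carry-over rule into the SAP and both Protocol endpoint lists.
- State that a Class I or III drug not taken before the index ablation has no allowed historic dose, so its continued use after blanking counts as failure whenever it was started.
- Align the third bullet of 13.7.1, which otherwise still requires a start after day 90.
- State the Kaplan-Meier failure date for a drug started in blanking and carried over.
- State how a drug stopped at the 3-month visit is counted. That visit's window is days 91 to 121, so a rule that fails any use on day 91 would also fail subjects whose drug is stopped at the scheduled visit.
- Report a sensitivity analysis under the other classification, with the number of subjects affected.

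Treatment during blanking is unchanged, and no view is taken on which drug use is clinically right.

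The cost is a SAP revision and a Protocol amendment with its approvals, and the stated success rate may be slightly lower. Drug names and start and stop dates are already collected. The list of collected items in Protocol 13.7 does not name dose, which the carry-over rule needs for previously used drugs, so the case report form should be checked for it.

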6.2.2.3. Analysis Methods

The probability of a subject achieving effectiveness success at 12 months (365 days) will be estimated using survival analysis, the Kaplan-Meier method. The standard error will be approximated using Greenwood's formula. A two-sided 95% log-log confidence interval for the probability will be constructed. For every treated subject, day 0 is defined as the day of the index cryoablation procedure. For subjects with treatment failure, the survival date will be set to the date of the treatment failure. For subjects without treatment failure through 12 months, those subjects will be censored at the last study contact date recorded on CRF which may include the last study visit, the exit date, or death date. If a subject without a treatment failure is lost to follow-up, the censoring date will be set to the last known study visit date.

For the component of the endpoint, documented AF/AT/AFL, if this documentation resulted from rhythm monitoring occurring at the 12-month visit within the 12-month visit window, the date of recurrence will be set to 365 days from the study ablation procedure so that these events will be counted as treatment failures in the 12-month Kaplan-Meier analysis. This objective will be analyzed in the mITT dataset: all enrolled subjects who have the Arctic Front Advance Cardiac CryoAblation Catheter inserted into vasculature will be included.

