13.12. Holter and TTM Management

Market-released Holvers will be distributed by a core lab to centers after activation has occurred. All subjects will wear a Holter in conjunction with their 6 and 12 month office visits. Holvers will then be sent back to the center after they have been worn by the subject. The core lab will be responsible for adjudication of atrial arrhythmias for the primary objective of the study. The core lab will manage maintenance, calibration and tracking of the Holvers.

Holter distribution logs will be provided to European centers. The logs must be maintained and updated when Holvers are received and returned to the core lab.

Market-released TTMs will be distributed by a core lab to centers after activation has occurred. All subjects will transmit weekly and symptomatic ECGs via the TTM system following their 3 month office visit. The TTM system will be sent back to the core lab at the end of the study. The core lab will be responsible for adjudication of atrial arrhythmias for the primary objective of the study. The core lab will manage maintenance, calibration and tracking of the TTMs.

TTM distribution logs will be provided to European centers. The logs must be maintained and updated when TTMs are received and returned to the core lab.

13.13. 12 lead Electrocardiograms

Market-released 12-lead ECG machines will be distributed by a core lab to centers after activation has occurred. All 12-lead ECGs starting with the one occurring at the 3 month office visit will be sent to the core lab. The 12-lead ECG machine will be sent back to the core lab at the end of the study. The core lab will be responsible for adjudication of atrial arrhythmias for the primary objective of the study. Copies of additional source documents may be requested. The core lab will manage maintenance, calibration and tracking of the 12-lead ECG machine.

12-lead ECG distribution logs will be provided to European centers. The logs must be maintained and updated when 12-lead ECG machines are received and returned to the core lab.

13.14. [REDACTED]

Follow Appendix B if the subject is enrolled in the sub-study [REDACTED]

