Kojodjojo P, et al Heart 2010;96(17):1379-1384. ^v	Prospective, consecutive patients	1	34	3M,6,12 and every 6 thereafter (24h Holter + ECG +symptomatic event recorder)	Any AF/AT > 30s	0.48 (0.30, 0.65)	YES	83%
Kubala M, et al Clin Electrophysiol 2011;34(7):837-843. ^{vi}	Prospective, consecutive patients, PVI-only	1	33	ECG and 24hr Holter @ 1M,3M,6M,12M and symptomatic event recorder	AF > 30s	0.52 (0.34, 0.69)	YES	Not reported

Medtronic Confidential

STOP Persistent AF Clinical Investigation Plan

Version 6.0, 01DEC2017 Page 68 of 128

Malmborg H, et al Europace 2013;15(11):1567-1573. ^{vii}	Prospective, randomized, PVI-only	1	15	ECG @ 3M,6,12 and 7 day Holter @ 6M,12M	AF > 30s	0.60 (0.32, 0.84)	NO	98%
Neumann T, et al J Am Coll Cardiol 2008;52(4):273-278 ^{viii}	Prospective, consecutive patients, PVI-only	3	53	7 day Holter @ 3M,6M,9M,12M	AF > 30s	0.42 (0.28, 0.56)	YES	97%
Schmidt M, et al Int J Cardiol 2013;167(1):114-120 ^{ix}	Consecutive patients, PVI-only	3	44	ECG and 72hr Holter @ 1M,3M,6M,9M,12M and symptomatic event recorder	AF or Flutter >30s	0.77 (0.62, 0.89)	YES	100%
Schmidt M, et al Clin Res Cardiol 2012;101(10):777-785. ^x	Prospective, consecutive patients, PVI-only	1	33	ECG and 72hr Holter @ 1M,3M,6M,9M,12M and symptomatic event recorder	AF > 30s	0.70 (0.51, 0.84)	NO	98.40%
Lemes C, et al Europace. 2015 May 19. [Epub ahead of print]. ^{xi}	Retrospective, PVI-only	2	49	Holter and ECG and telephonic interviews @ 3M,6M,12M	Any AF/AT > 30s	0.69 (0.57, 0.83)	YES	100%
Weighted average (weights based on study sample size)						59.3% (43.8, 74.4%)		

*Confidence interval calculated with binomial Fisher's exact methods

Medtronic Confidential

Sample Size Calculation

For the US/Canada/Europe cohort, 150 treated subjects affords 90% power based on the following assumptions:

- One analysis at 12-months
- 12-month efficacy rate = 54%
- OPC = 40% at 12-months
- Overall alpha = 0.025, one-sided
- 10% attrition through 12 months
- Binomial exact methods

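### For subjects lost to follow-up, rhythm-monitoring time after the last visit counts only if it ends in failure, which slightly lowers the estimated 12-month success rate

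*SAP*

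**What the plan says.** SAP 6.2.2.3 and Protocol 17.3.1 carry the same rules. A subject with treatment failure enters the Kaplan-Meier analysis at the date of failure, whether or not that date follows the last visit. A subject without failure is "censored at the last study contact date recorded on CRF which may include the last study visit, the exit date, or death date". A separate sentence then covers one group: "If a subject without a treatment failure is lost to follow-up, the censoring date will be set to the last known study visit date".

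A recurrence of at least 30 seconds on TTM after day 90 is a failure (SAP 6.2.2.2). Protocol 13.12 states: "All subjects will transmit weekly and symptomatic ECGs via the TTM system following their 3 month office visit". Office visits after blanking have targets at days 91, 180 and 365 (Protocol Table 8), so up to about six months of TTM can follow a last visit.

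Two other places describe the data differently. Protocol 13.19 commits to analysing everything available up to exit. SAP 6.4 says subjects with short follow-up contribute until their last contact. Protocol 13.19 lists loss to follow-up and withdrawal as separate exit reasons.

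**The concern.** Kaplan-Meier requires events and time at risk to be counted over the same period. Take a subject who attends month 3, transmits until month 9 and is then lost. AF on a month-7 TTM is a failure at month 7. If every TTM is clean, the subject is censored at month 3. After month 3 this subject is in the risk set only if a failure occurs, so the censoring date depends on the outcome and the estimated failure rate is too high.

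A failure-free subject who withdraws may instead be censored at exit. If rhythm monitoring ended earlier, the unmonitored interval is credited as failure-free and the error runs the other way. At stake is the estimate whose lower confidence bound is compared with the 40% goal.

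**Working it through.** **Inputs from the documents.** One-sided level 0.025 (SAP 6.2.2.1). Goal 40%, assumed success 54%, 150 treated and "10% attrition through 12 months" (Protocol 17.3.1). Kaplan-Meier at day 365 with Greenwood standard error and log-log 95% interval (SAP 6.2.2.3).

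**Assumptions not in the documents.** Exit is uniform over days 92–364. The last visit is day 91 if exit is before day 180, otherwise day 180. All leavers are treated alike. The 10% attrition is taken as the share of leavers.

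**Step 1: the plan's own figure.** 150 × 0.9 = 135. The smallest r with P(X ≥ r | 135, 0.40) ≤ 0.025 is 66 (actual level 0.0224), and P(X ≥ 66 | 135, 0.54) = 0.899. For 148 subjects r = 72, level 0.0202, power 0.917. Both match SAP 7.1. This binomial calculation uses no censoring dates, so the point does not affect it.

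**Step 2: hand calculation, TTMs continuing to exit.** Assume a constant hazard after day 90: λ = −ln(0.54)/275 = 0.6162/275 = 0.002241 per day.
- Stayer: 0.46 expected failures and 0.46/λ = 205.3 expected days at risk.
- Leaver: averaging 1 − exp(−λ(x − 90)) over exit days x = 92 to 364 gives 0.2545 failures and 0.2545/λ = 113.6 days at risk.
- Clean time discarded per leaver: averaging (x − last visit) × exp(−λ(x − 90)) gives 51.4 days.

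With 10% leavers:
- Failures per subject: 0.9 × 0.46 + 0.1 × 0.2545 = 0.4394.
- Full exposure: 0.9 × 205.3 + 0.1 × 113.6 = 196.1 days. Success = exp(−275 × 0.4394/196.1) = 54.0%.
- Lost-to-follow-up rule: 196.1 − 0.1 × 51.4 = 191.0 days. Success = exp(−275 × 0.4394/191.0) = 53.1%.

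The gap is 0.9 points. With 5% leavers the same steps give 0.4497 failures over 200.7 or 198.1 days, so 54.0% against 53.6%, a gap of 0.4 points.

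**Step 3: simulation of the planned test.** True success is 54% and leavers 10%. Model A has 3% acute failures; of the rest, 0–30% fall at day 91, 0–20% at day 365 and the remainder evenly. Its estimates use 1,000,000 subjects; its power and level use 8,000 trials of 150 with 15% at day 91 and 15% at day 365. Model B has a constant hazard after day 90, with 4,000 trials of 150 per setting.

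| Rule | Monitoring | Estimate, A / B | Power, A / B | One-sided level at true 40% |
|---|---|---|---|---|
| Lost to follow-up | TTM to exit | 53.1–53.5% / 53.0% | 87.6% / 86.0% | 0.017 (A) |
| Censor at exit | TTM to exit | 53.9–54.0% / 53.9% | 90.4% / 90.0% | 0.024 (A) |
| Censor at exit | TTM stops at last visit | 54.4–54.9% / 55.0% | 92.7% (A) | 0.035 (A), 0.046 (B) |
| Last visit for events and censoring | either | 53.9–54.0% (A) | 89.9% (A) | 0.024 (A) |

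The first two rows use the same data and differ by 0.5–0.8 points (A) or 53.9 − 53.0 = 0.9 (B). Power differs by 90.4 − 87.6 = 2.8 or 90.0 − 86.0 = 4.0 points. The Monte Carlo standard error of a power figure is about half a point: √(0.86 × 0.14/4000) = 0.0055. With 5% leavers the model A gap is 0.2–0.4 points.

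**The case against.** The strongest reply is that the effect is small and works against the device. The first part stands as to size: even the upper case is under a point, against a 14-point margin between 54% and 40%. The second also stands: the lost-to-follow-up rule makes the test conservative (level about 0.017), so it cannot manufacture a positive result. Many lost subjects will also stop transmitting when they stop attending, and then nothing is discarded.

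A reader might infer that the exit label alone moves the estimate by 1–3 points. A gap that wide compares lost subjects who keep transmitting with withdrawn subjects whose monitoring stopped months before exit, which are two different monitoring patterns.

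A reader might also infer that exit-date censoring is a fixed rule, or that sites are free to pick the label. The SAP only says the last contact may include the exit date, and the core lab also enters its data on CRFs (Protocol 13.17), so a TTM could qualify as a contact. Loss to follow-up requires at least two recorded contact attempts, while withdrawal is the subject's decision (Protocol 13.19). An exit visit with a 12-lead ECG should be attempted (Protocol 13.11, 13.19 and Table 7, note 6), which narrows the upward error. It does not remove it, because the visit is only to be attempted and a missed weekly TTM is not a deviation (Protocol 13.18).

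The tipping-point analysis (Protocol 17.3.1, SAP 6.4) is no remedy. It asks how many early leavers would have to fail to cross 40%, and leaves the censoring in the primary estimate unchanged.

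**Conclusion.** The concern holds for the lost-to-follow-up sentence. Read as written, it keeps TTM time after the last visit only when that time ends in failure, and it cannot be squared with Protocol 13.19 or SAP 6.4. At the planned 10% attrition it lowers expected success by about 0.5–0.9 points and power by about 3–4 points; at 5% leavers the shift is about 0.2–0.4 points. These are upper cases, since they take every leaver as lost with TTMs continuing to exit.

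The upward error for other leavers is secondary and conditional: up to about 1 point at 10% leavers, with the one-sided level rising to about 0.035–0.046, if monitoring stopped at the last visit and no exit ECG was obtained. Neither error invalidates the design or the stated 90% power. The reason to act is that a primary estimator should not have a censoring date that depends on the outcome, and the repair is cheap.

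**What to change.** In SAP 6.2.2.3 and Protocol 17.3.1, replace the lost-to-follow-up sentence with one rule. Every failure-free subject who leaves before 12 months, whatever the exit reason, is censored at the last date endpoint status was assessed, meaning the last core-lab-readable TTM, Holter or 12-lead ECG, including an exit-visit ECG. Apply the same cut-off to failures in early leavers, so that events and exposure cover the same period. This second half is needed because drug and re-ablation failures are learned at site contacts. Counting one that falls after the last recording, while censoring clean subjects at that recording, would recreate the problem on a smaller scale.

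Align Protocol 13.19 and SAP 6.4 with the new wording.

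The cost is a short text change. The core lab already holds the recording dates in a study database (Protocol 13.17), so no new data are needed. The downside is that drug and re-ablation status between the last site contact and a later TTM is less certain. Add a sensitivity analysis that cuts both events and censoring at the last site visit. The safety analysis (SAP 6.2.3.3) has the same sentence, but TTM does not bear on those events.
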